9.3 Study Records

9.4 Use of Information and Publications

10. References

Couple-Based Motivational Interviewing with Mobile Breathalyzers to Reduce Alcohol Use in South Africa

Study Investigators

[name]

Principal Investigator

Center for AIDS Prevention Studies

University of California, San Francisco

[name], PhD

Site Principal Investigator

Human and Social Development Programme

Human Sciences Research Council

[name]

Co-Investigator

Department of Psychology

Hunter College, City University of New York

[name]

Co-Investigator

Center for AIDS Prevention Studies

University of California, San Francisco

[name]

Co-Investigator

Center for AIDS Prevention Studies

University of California, San Francisco

Couple-Based Motivational Interviewing with Mobile Breathalyzers to Reduce Alcohol Use in South Africa

SCHEMA

Design: Formative qualitative phase followed by pilot randomized controlled trial

Population: Heterosexual couples with at least one heavy alcohol drinker on antiretroviral therapy

Study size: 40 key stakeholders and 90 couples/180 individuals (220 people total)

Study duration: 36 months

Aim 1: To develop a couple-based Motivational Interviewing intervention with mobile breathalyzer technology to deliver real-time feedback on blood alcohol content (BAC) levels. We will target heavy alcohol users with HIV and enroll their primary partner.

Aim 2: To develop and pilot test the study procedures for a future randomized controlled trial (RCT) of the couple-based intervention. We will develop and pilot test: a) training procedures; b) randomization procedures; c) the pilot study procedures; and d) data collection instruments.

Aim 3: To determine the feasibility and acceptability (F&A) of couple-based MI as a standalone intervention and when combined with mobile breathalyzers with couples to provide real-time feedback and support.

Study Site: Vulindlela/Sweetwaters community, KwaZulu-Natal, South Africa

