phones to be provided. Our intervention may not be appropriate for couples experiencing severe IPV. We will exclude those who fear for their safety by participating in the study and/or report severe IPV in the past 3 months using the WHO measure for South Africa, which assesses physical, sexual, and emotional violence, and determines whether it is mild, moderate, or severe. The WHO measure for IPV contains 8 questions that assess perpetration and victimization of 4 types of severe violence including physical (kicking, punching, hitting, beating, scalding, burning), threats using weapons such as a gun or a knife, and restraint (i.e. holding down) in the past three months. The WHO questions on IPV will be administered to both members of the couple. Couples-based interventions in South Africa have successfully employed this approach. We believe this approach balances sample generalizability with safety. If couples report any IPV (mild, moderate, or severe) during screening or over the study, we will follow an established protocol to assess safety, provide emotional support, and provide intervention and/or linkage to psychological and/or medical services. If either person in the couple declines to participate, the couple as a whole will be ineligible.

[name] prior work with couples in this community in KZN showed that less than 1% of female partners reported any alcohol use, with the primary drinker almost always being the male partner. As such, we will not exclude dual-drinking couples since these couples could really benefit from the intervention. However, should we enroll couples with two heavy alcohol drinkers, our couple-based MI approach is designed to be flexible to handle cases where both partners are heavy drinkers, and will consider change behavior in both partners. The software for the breathalyzer is not optimized for both partners being "testers" and "accountability partners." Therefore, in couples with two qualified drinkers, whichever one is screened first will be considered the "index patient" and get the breathalyzer. In couples with two heavy drinkers on ART, both partners will have blood draws for viral load and/or alcohol use at follow-up visits.

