5.9 Control condition. Participants will receive the Usual Care (UC) defined by the South African national 2019 ART Clinical Guidelines (updated in March 2020). The harms of alcohol use are briefly discussed during the morning health talks in the waiting rooms of HIV clinics. HIV clients are advised that alcohol intake should be reduced to <2 standard drinkers/day for men and <1 for women for 5 out of 7 days per week. After randomization, couples in the control arm will receive brief alcohol counseling modeled off WHO guidelines and [name] intervention in Malawi, which uses participants' baseline AUDIT scores for messaging around alcohol reduction and lasts 5-10 minutes. In selecting the control, we chose to balance our ethical obligation to provide basic health information on alcohol use (minimal in this setting), while maximizing the generalizability of our findings to inform a future RCT, which will employ a UC control group. Clinical trial experts recommend the UC condition over other designs such as a time-and-attention control (TAC) when the long-term goal is to inform implementation science and scale-up. Our long-term goal will be to test the effectiveness of a scalable alcohol intervention. Moreover, because TAC designs have an active but different intervention, there is the risk of positively-biased intervention results because the comparison arm can distract participants from making reductions in alcohol use they would have otherwise made.

5.10 Procedures for mobile breathalyzers with couples in MI *Plus* arm. Drinkers will be provided with handheld breathalyzers and both partners will receive access to the breathalyzer results. Drinkers will receive SMS requests to take a breathalyzer test twice per day (e.g., in the morning at 11 am and in the evening at 8 pm). After the drinker completes each breathalyzer test, the partner receives a notification that the drinker completed a test and can view the test results. Partners will receive a unique login username and password linked to their study ID. [name] and the research manager(s) will facilitate a 1-2 hour training for couples how to use the breathalyzers/phones (e.g., charging, Wi-Fi, Bluetooth), complete breathalyzer tests, app functionality, trouble-shooting issues, and technical support. Couples will be instructed to use the breathalyzers for a 60-day period. Assessments at 60 days will allow us to assess the effects on alcohol use immediately following the 60-day intervention period.

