A technology navigator will monitor daily compliance and check-in with participants to assist with login credentials, lost or damaged devices, cellular connectivity, difficulties using the phones or breathalyzers, and intentional non-use of the breathalyzers—with close monitoring during the first week. Navigators will monitor for safety issues and IPV (interpersonal violence) during routine check-ins and will provide assistance should a safety/IPV issue arise.

5.11 Survey assessments. Assessment visits will be held in community-based locations such as youth centers or in our team's mobile caravans used in other couples' studies. To minimize loss-

Couple-Based Motivational Interviewing with Mobile Breathalyzers to Reduce Alcohol Use in South Africa

to-follow-up, we will administer follow-up surveys over the phone in the case that a participant moves out of the area or is unavailable for an extended period of time. For the pilot study, surveys will be administered at baseline and 2-months (after receiving all MI sessions and/or using the breathalyzers for 60 days), and 6-months post-intervention initiation. Measures collected will be the same across visits with the exception of time-invariant variables such as demographics (collected at baseline only). All measures will be pre-tested, tailored for South Africa, and translated to *isiZulu* and back-translated to English. See Appendix with full survey instrument. Survey assessments will be interviewer-administered on tablet devices using REDCap mobile, last around 90 minutes, and uploaded to a secure web-based storage system. Partners will be assessed separately, but simultaneously, in private interview rooms.

	Domain	Measure (alphas noted are from prior studies with couples)
Primary outcomes (future trial)	Alcohol use	Number of drinking days in past 21, assessed using the three-week timeline follow-back method (TLFB) confirmed with the PEth biomarker.[32] AUDIT-C positive (score of ≥ 4 for men and ≥ 4 for women) and/or PEth positive (≥ 35 ng/ml).[33, 34]

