5.14 Exit interviews

Sampling: To contextualize the feasibility and acceptability data, we will conduct 60-90 minute exit interviews with 15 couples at the 2-month follow-up. Around five couples will be recruited from each arm, purposively sampled by participation level. For Arm 2, participation will be categorized as: low=attended one MI session, medium=attended two sessions, and high=attended all three sessions. For Arm 3, we will aim to enroll couples with varying test completion rates, categorized as low=completed less than 70% of breathalyzer tests, medium=completed 70-85% of tests, and high=completed>85% of tests. We will also try to interview couples in which both partners were heavy alcohol users to further understand how the intervention impacts dual drinkers.

Interview questions: We will elicit information on intervention preferences and satisfaction with domains of the intervention (e.g., frequency of breathalyzer tests and MI sessions, length, content, format of MI sessions). To explore dyadic mechanisms of change, we will elicit information on whether and how the breathalyzers and MI sessions enhanced communication, communal coping, and support. We will also elicit information on technology issues (e.g., user app experience, network connectivity, load shedding and power outages, battery life, trouble with logins) and contextual issues (e.g., literacy, alcohol stigma). Given the central question of whether the mobile breathalyzer technology can be used with couples to trigger support, we will assess how knowledge of BAC levels impacts the relationship (e.g., increases in couple conflict, changes in communication), how both partners interpret and respond to BAC levels, and the types of partner support provided and when.

Couple-Based Motivational Interviewing with Mobile Breathalyzers to Reduce Alcohol Use in South Africa

Procedures: Given the gender-power dynamics in this setting, the PI [name]'s prior qualitative research, and the potential bias (e.g., women not feeling comfortable voicing their opinions in front of male partners) and increased risk for violence that could result from interviewing partners together, we will interview both partners separately, but simultaneously. Interviews will be audio-recorded, transcribed word-for-word, and translated from *isiZulu* to English, and imported into Dedoose for analysis.

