7.0 STATISTICAL CONSIDERATIONS

7.1 Analysis of FGDs to refine the intervention. Using a template analysis approach [50], we will develop a pre-determined template based on elements of the intervention to retain or refine, and new elements to add to address the needs of the target population. Study investigators will generate a draft of the template with thematic codes for relevant domains of the intervention, and will independently code the FGD transcripts. The investigative team will then discuss the emerging themes, identify areas for further adaptation, and refine the intervention manual. Depending on the extent of the changes, we may hold a meeting with HSRC's CAB to review

Couple-Based Motivational Interviewing with Mobile Breathalyzers to Reduce Alcohol Use in South Africa

the FGD findings and identify intervention content and procedures that need to be added, removed, or refined.

7.2 Feasibility and acceptability data analysis. Our primary objective is to evaluate F&A of the intervention and study procedures. The primary analyses will include descriptive statistics of F&A indicators, comparing each statistic (e.g., percent retained) to the threshold listed in Table 4. Above-threshold findings will suggest a reasonable level of F&A while below-threshold findings would suggest that remedial modifications to study procedures and/or design would be required prior to moving forward with a full-scale trial. We will stratify the statistics by gender to consider sex as a biological variable.

Couple-Based Motivational Interviewing with Mobile Breathalyzers to Reduce Alcohol Use in South Africa

Table 4. F&A Domain	Measure	Threshold	Arm(s)
Recruitment	Number of couples enrolled per week	Average 5 per week/20 per month	All
Enrollment	Proportion of eligible couples who enroll and complete baseline assessment	80% of eligible couples will complete enrollment	All
Randomization	Proportion of enrolled couples who complete randomization process	90% of enrolled couples will complete randomization	All
Participation	Proportion of couples who attend 66% and 100% of MI sessions	100% of couples will attend 66% (2 out of 3) of sessions; 75% of couples will attend all 3 sessions	2, 3

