Engagement with mobile breathalyzer technology	Proportion of breathalyzer tests taken after prompted; number of partner SMS messages sent and received on BAC results; number of drinker SMS reminders to take breathalyzer tests sent and received; average length of time to take breathalyzer tests after prompted; average number of app logins per week to access BAC data (for both partners); average user session length; number of lost/stolen phones and breathalyzers	70% completion rate	3
Retention	Retention rates; reasons for dropouts	85% retention at 2-month follow-up	All
Process outcomes	Length of MI sessions in minutes	≤90 minutes per session[9]	2, 3
Intervention fidelity	Expert ratings of quality of intervention using audio-recorded intervention sessions (checklists)	>80% inter-rater reliability	2, 3
Assessment procedures	Length of surveys; proportion of couples who complete baseline, 1, 2, and 6-month surveys	90 minutes; 75% of all couples will complete all assessments	All

Couple-Based Motivational Interviewing with Mobile Breathalyzers to Reduce Alcohol Use in South Africa

Acceptability	Proportion of couples satisfied with the intervention. Couples will decide their satisfaction together since this is a dyadic intervention.	75% of couples reporting being satisfied or very satisfied	All
---------------	---	--	-----

Couple-Based Motivational Interviewing with Mobile Breathalyzers to Reduce Alcohol Use in South Africa

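### Table 4 measures acceptability by one satisfaction rating that the couple agrees on together, which is open to a bias section 5.14 guards against and, as defined, cannot be split by gender as section 7.2 says

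*Combined protocol and SAP*

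**What the plan says.** Section 7.2 makes feasibility and acceptability the primary objective. The primary analysis is descriptive and compares each indicator with its Table 4 threshold. The acceptability row takes the proportion of couples satisfied with the intervention, against 75%, in all arms. It specifies how the rating is obtained: "Couples will decide their satisfaction together since this is a dyadic intervention". Section 4.0 likewise treats the couple as the unit of both intervention arms.

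Three other places bear on this:

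- Section 7.2, on the same indicators: "We will stratify the statistics by gender to consider sex as a biological variable". No exception is made for couple-level rows.
- Section 5.14, on the content of the exit interviews: "We will elicit information on intervention preferences and satisfaction with domains of the intervention". On procedure, it separates partners because of gender-power dynamics, the risk of violence and a possible bias, with the example "women not feeling comfortable voicing their opinions in front of male partners".
- Section 5.11, on the surveys: "Partners will be assessed separately, but simultaneously, in private interview rooms".

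The Schema gives the population as "Heterosexual couples with at least one heavy alcohol drinker on antiretroviral therapy".

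**The concern.** The protocol names a reason why a woman may not state her view in front of her partner, and it acts on that reason when it asks about satisfaction in the exit interviews. The indicator that is compared with a threshold asks the couple to settle one answer together. The stated reason, that the intervention is dyadic, explains why a couple-level measure is wanted. It does not deal with the bias.

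Partners may well have different views because their roles differ. Section 3.1 reports from earlier work in this community that couples drank unevenly, "with the primary drinker almost always being the male partner". In the breathalyzer arm the drinker takes the tests; section 5.10 says that "the partner receives a notification that the drinker completed a test and can view the test results". One partner is monitored and the other does the monitoring, and mostly these will be the man and the woman respectively.

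At stake is a primary-objective indicator that can hide one partner's dissent and, as defined, cannot show whether men and women differ. No sample size, alpha level, hypothesis test or safety rule is affected.

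**Working it through.** **Side-by-side reading**

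1. Topic: Table 4 and section 5.14 both cover satisfaction with the intervention.
2. Setting: the Table 4 rating is decided together, whereas the exit interviews and surveys are held apart.
3. Gender: each heterosexual couple has one man and one woman, so one rating per couple holds no separate male and female values. Splitting by the index patient's gender would be a different statistic that section 7.2 does not describe.
4. Other rows: recruitment, enrollment, randomization and session attendance are also counted by couple and share this limit. They count events, whereas satisfaction is an opinion that each partner can hold separately.

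**Illustration of size**

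The 75% threshold is a preset benchmark with no derivation in the documents, so there is no figure to reproduce. The inputs from the documents are 30 couples per arm (section 2.5) and 75% (Table 4). All satisfaction counts below are assumed. I also assume that every couple answers and that couples who agree report their shared view.

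- Couples needed: 0.75 × 30 = 22.5, so 23 (23/30 = 76.7%; 22/30 = 73.3% falls short).
- Assumed private views: both satisfied 18, only the man 7, only the woman 1, neither 4 (total 30).
- Men satisfied: (18 + 7)/30 = 25/30 = 83.3%.
- Women satisfied: (18 + 1)/30 = 19/30 = 63.3%.
- Lowest joint rate, if every disagreeing couple reports the unsatisfied view: 18/30 = 60.0%.
- Highest joint rate, if every disagreeing couple reports the satisfied view: (18 + 8)/30 = 26/30 = 86.7%.
- Threshold met if at least 23 − 18 = 5 of the 8 disagreeing couples report the satisfied view.

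If the sexes are swapped (only the man 1, only the woman 7), the joint range is unchanged, so the joint figure cannot tell the two situations apart.

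More generally, with d disagreeing couples, the result depends on how they settle their answer when the both-satisfied count B satisfies B ≤ 22 and B + d ≥ 23:

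| d | B (of 30) |
|---|---|
| 2 | 21 to 22 |
| 4 | 19 to 22 |
| 6 | 17 to 22 |
| 8 | 15 to 22 |

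**Precision per arm**

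The 95% Wilson interval is [p + z²/2n ± z√(p(1−p)/n + z²/4n²)] / (1 + z²/n). With p = 23/30, n = 30 and z = 1.96, it is (0.8307 ± 0.1643)/1.1281, or 59% to 88%.

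Private ratings would give 30 men and 30 women per arm. The approximate 95% half-width for either gender at 75% is 1.96 × √(0.75 × 0.25/30) = 0.155, or 15.5 percentage points.

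**The case against.** The joint rating is a deliberate choice with a stated reason, and a shared verdict on a couple intervention is a legitimate measure. That stands, and is why the joint rating should be kept.

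Section 5.14's reasoning is written for interviews of 60 to 90 minutes that probe conflict and reactions to alcohol readings, and it also rests on the risk of violence. Applying it to one short rating is an extension. What carries over is the point about voicing an opinion in front of a partner on the same subject.

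The separate exit interviews in 15 couples already give private views from both partners and are reviewed together with the quantitative results. This is real mitigation, but the sample is small and purposive, the data are qualitative, and they do not feed the 75% figure.

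The gender sentence in section 7.2 may be meant only for indicators measured on individuals. If so, it needs to say so.

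A reader might go further in three ways that the documents do not support:

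- That the trial's data cannot show a gender difference in satisfaction. Section 5.11 refers to an appendix with the full survey instrument, which was not available. An individual item may already be there.
- That the joint rate will be too high. Deference to the man raises or lowers it according to his view.
- That All in the arms column means one pooled rate. No text says so. Section 2.5 and Aim 3 point to satisfaction with each intervention arm, and collecting the item from control couples, who receive brief counseling, is coherent.

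**Conclusion.** The concern holds as a minor point about one indicator. As defined in Table 4, acceptability is open to the partner-present bias that section 5.14 names, and it cannot be stratified by gender as section 7.2 says. The first limb establishes susceptibility only: the documents do not show that bias will occur, in which direction, or how large it would be. The gender limit is shared with other couple-level rows and matters most here because satisfaction is an opinion.

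The 60.0% to 86.7% range rests wholly on assumed counts and on all 30 couples in an arm answering. It shows how far a joint figure can move with the way couples settle disagreement; it is not a forecast. Consequences are limited because the thresholds are descriptive, and a shortfall would suggest changes to procedures or design before a full trial.

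**What to change.** Check the survey instrument first. If it has no individual satisfaction item, ask each partner the item privately at the 2-month survey, where partners are already assessed apart. Table 4 gives no time point for the rating, so that placement is a proposal.

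Then amend section 7.2 and Table 4 as follows:

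- Report the percentage satisfied or very satisfied by gender and by arm next to the joint rating, with the number of couples whose partners disagree.
- Keep the joint rating against 75%. If a couple-level rule derived from the private ratings replaces it, such as both partners satisfied, pre-specify that rule, including how a couple counts when only one partner answers, and restate the threshold. The 75% was set for a joint rating and should not be carried over to a stricter rule unexamined: in the illustration above, both-satisfied is 60.0%.
- Say which Table 4 statistics are stratified by gender.
- State that the All entry is read arm by arm, consistent with section 2.5 and Aim 3.

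The cost is one extra survey item and a few lines of text. Private or both-satisfied figures may look less favourable than the joint one, and per-arm intervals will be wide.

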2.5 Study design

For Aim 1, we will adapt a couple-based MI framework and interventions developed by co-I [name] (*We Test* and the *Couples Health Project*) to address alcohol use in heavy alcohol users and their primary partners and incorporate the mobile breathalyzer component. We will follow the ADAPT-ITT framework by conducting focus group discussions (FGDs) with around 40 key stakeholders to gain feedback on the intervention and then refining the intervention. For Aim 2, we will develop training procedures, study procedures, and data collection instruments that will be pilot tested during the RCT. For Aim 3, we will conduct a three-arm RCT with 30 couples randomized to the following arms (90 couples total): 1) an enhanced usual care control condition; 2) couple-based MI; and 3) couple-based MI with mobile breathalyzers for real-time feedback. For arm 2 and 3, couples will receive 3 MI sessions over a 60-day period with an experienced counselor to help strengthen communication and problem-solving skills around alcohol use. For Arm 3, couples will use the mobile breathalyzers and app for 60 days and receive the same MI sessions, which will also incorporate feedback on BAC levels (prior 30 days) and teach couples how to effectively engage with the breathalyzers. This design will allow us to assess the effectiveness of couple-based MI alone and the added synergistic effect of the mobile breathalyzers on alcohol use and HIV outcomes (e.g., adherence to antiretroviral therapy (ART), viral suppression). Our F&A outcomes will include enrollment and retention rates, satisfaction with both intervention arms, MI session attendance rates, and follow-up survey completion rates. We will also conduct qualitative interviews with a subset of 15 couples to contextualize F&A data and refine the intervention and procedures for a future full-scale efficacy trial.

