4.0 Intervention Description

The two intervention arms consist of standalone MI (arm 2) and MI *Plus* (arm 3), which consists of MI sessions in arm 2 plus use of the mobile breathalyzer and app for two months. Both intervention arms are conducted with the couple as a unit.

MI *Plus* will consist of: 1) manualized MI sessions with couples and a counselor; 2) handheld breathalyzer with accompanying mobile app to deliver real-time feedback on drinkers' BAC levels to both partners. BAC data collected will be also used to provide personalized feedback based on summarized displays (e.g., calendar) of BAC levels in the MI sessions.

MI Sessions: We will aim for around 3 in-person sessions over a 60-day period with each session lasting 60-75 minutes – consistent with the format used in the Couples Health Project. We will administer MI sessions that are structured and manualized, as a roadmap for moving through content. MI is a collaborative process between a counselor and client, aimed at exploring and resolving ambivalence towards changing a behavior. Our approach will center around four MI processes (engagement, focusing, evoking, and planning)[30] and a fifth process around relationship quality based on co-I [name]' MI framework for couples[19, 20]. [name] recently published a paper using qualitative data from a couple-based MI intervention that supports the necessity of including relationship quality as a fifth MI process when working with couples.[31] An exploration of dyadic strengths is necessary to support couples with divergent views in the resolution of interpersonal ambivalence and the development of shared goal. [name] developed structured activities for exploring couples' shared goals and a lexicon of counselor skills that are effective in responding to dyadic ambivalence and achieving accommodation.[20]

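### Table 4 judges satisfaction with the intervention over all three arms, although control couples do not receive it and Section 2.5 limits the outcome to the two intervention arms

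*Combined protocol and SAP*

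**What the plan says.** The measure in the Acceptability row of Table 4 is "Proportion of couples satisfied with the intervention", and the threshold is "75% of couples reporting being satisfied or very satisfied". Each couple gives one joint answer: "Couples will decide their satisfaction together since this is a dyadic intervention". The Arm(s) column reads *All*.

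Elsewhere in the table that column is used selectively. Session participation, MI session length and fidelity are limited to arms 2 and 3, and breathalyzer engagement to arm 3. Section 7.2 compares each statistic with its Table 4 threshold and plans a breakdown by gender only.

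Three other places bear on the row:

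- Section 2.5 lists the outcome as "satisfaction with both intervention arms". Section 4.0 identifies the intervention arms as arms 2 and 3.
- Aim 3 in the Schema is to determine the "feasibility and acceptability (F&A) of couple-based MI as a standalone intervention and when combined with mobile breathalyzers".
- Section 5.9 says what arm 1 gets beyond usual care: "After randomization, couples in the control arm will receive brief alcohol counseling". It lasts 5 to 10 minutes and includes no MI sessions and no breathalyzer.

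**The concern.** A third of the couples covered by *All* have not received what the row asks about. The document does not say what a control couple would be rating, or how the arms are combined into one percentage.

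If they are pooled, the result mixes opinions of the comparator with opinions of two different interventions. Satisfied control couples can lift a poorly liked intervention over 75%, dissatisfied ones can pull a well liked intervention under it, and a weak arm 3 can be carried by the other two arms. The planned gender breakdown gives no protection, since a rating agreed jointly by a man and a woman cannot be split by gender.

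Feasibility and acceptability is the primary objective, and this is the only satisfaction threshold in the table. Under Section 7.2 a below-threshold result points to changes before a full-scale trial, so a misleading percentage could prompt needless changes or leave needed ones unmade.

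**Working it through.** **Inputs.** Section 2.5 gives a "three-arm RCT with 30 couples randomized to the following arms (90 couples total". The threshold is 75% (Table 4). Expected satisfaction by arm is not given, so control satisfaction is varied from 50% to 100% as an assumption. The 75% is a chosen benchmark with no derivation to reproduce; the total does reproduce, as 3 × 30 = 90.

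**Pooled pass mark.** 0.75 × 90 = 67.5, so 68 satisfied couples are needed (68/90 = 75.6%).

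**Lowest combined MI result that passes.** This is 68 minus the satisfied control couples, out of 60.

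| Control satisfied | MI arms need | MI rate | Gap to 75% |
|---|---|---|---|
| 30/30 (100%) | 38/60 | 63.3% | 11.7 points below |
| 27/30 (90%) | 41/60 | 68.3% | 6.7 points below |
| 24/30 (80%) | 44/60 | 73.3% | 1.7 points below |
| 15/30 (50%) | 53/60 | 88.3% | 13.3 points above |

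Apart from rounding to whole couples, the rule is (c + 2m)/3 ≥ 0.75, with c the control rate and m the combined MI rate. Hence 0.75 − m ≤ (c − 0.75)/2: the MI arms can fall short by at most half of the control arm's excess over 75%.

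**One MI arm hidden by the other two.**

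- Control 30/30, arm 2 25/30, arm 3 13/30: 30 + 25 + 13 = 68, a pass with arm 3 at 43%.
- Control and arm 2 both 27/30: arm 3 needs 68 − 54 = 14/30 (46.7%).

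**Error in the other direction.** Control 15/30 with 52/60 (87%) in the MI arms: 15 + 52 = 67, and 67/90 = 74.4%, a fail.

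**Chance of passing.** These are exact binomial probabilities, assuming independent couples and the same true rate in both MI arms. The restricted rule needs 45/60.

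| True MI rate | Arms 2 and 3 only | Pooled, control 90% | Pooled, control 100% |
|---|---|---|---|
| 65% | 6.6% | 36% | 66% |
| 70% | 24% | 66% | 90% |

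**Other denominators.** With 85% retention (0.85 × 30 = 25.5, about 26 per arm), the pass mark is 59/78, and full control satisfaction lets the MI arms pass at 33/52 (63.5%). With the roughly 120 couples randomized under Section 5.7 (40 per arm), it is 90/120 and 50/80 (62.5%). The picture does not change.

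**The case against.** **Pooling is inferred.** No sentence says that the 75% is computed on one denominator of 90, and the Arm(s) column might only show where an item is collected. This stands as a caveat. If the threshold were applied within each arm, no arm could mask another. The conflict with Section 2.5 would remain, as would the undefined control rating.

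**Asking control couples may be deliberate.** Section 7.2 covers study procedures as well as the intervention, the control is enhanced by brief counselling, and exit interviews include every arm. That justifies collecting control satisfaction. It does not justify counting it as satisfaction with the intervention.

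**Stronger readings that the documents do not support.**

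- *That this row is a go/no-go rule.* Section 7.2 describes thresholds as suggesting adequate feasibility and acceptability or a need for modification, and this is one of ten rows.
- *That Aim 3 goes unanswered, or that a disliked breathalyzer arm would go unseen.* Section 5.14 samples about five couples per arm for exit interviews and asks about satisfaction with both components. Participation and breathalyzer engagement have their own thresholds. The interviews are qualitative, however, and do not enter the 75% comparison.
- *That both MI arms together could be far below 75%.* At 30 couples per arm the gap is at most 11.7 points and needs every control couple satisfied. If control satisfaction is 75% or less, pooling does not help the MI arms.
- *That the retention and assessment rows need the same change.* Every arm is retained and assessed, so *All* is right there.

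**A separate threshold per arm goes beyond Section 2.5.** That section supports restricting the row to arms 2 and 3, not splitting it. The case for splitting comes from Aim 3 and from arithmetic: 30/30 in one MI arm and 15/30 in the other give 45/60 = 75%, which still passes.

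**Conclusion.** The point holds as an internal inconsistency with a bounded numerical consequence. Table 4 names the wrong set of arms for what it measures, and Section 7.2 makes Table 4 the standard, so Section 2.5 shows the intent without correcting the rule.

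On the pooled reading, the two MI arms together could pass at 63% to 68% when control satisfaction is 90% to 100%. A single MI arm could be far lower, as in the 43% example. MI arms at 87% could fail because of a control arm at 50%. The larger risk is one MI arm hidden by the other two arms.

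These sizes rest on pooling, on 30 couples per arm and on illustrative satisfaction counts. The mismatch between Table 4 and Section 2.5 rests on none of them. It should be corrected before the acceptability result is reported.

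**What to change.** In Table 4, change the Arm(s) entry of the Acceptability row from *All* to *2, 3*, which brings it into line with Section 2.5. Add one sentence to Section 7.2: satisfaction will be reported for arm 2 and arm 3 separately, each against 75% (23 of 30 couples, since 0.75 × 30 = 22.5), and control couples' satisfaction with enhanced usual care and the study procedures will be described without a threshold.

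This costs one table cell and one sentence and needs no additional couples. The downside is precision. At 75%, the approximate 95% half-width is 1.96 × √(0.75 × 0.25/30) = 15.5 percentage points for one arm, against 1.96 × √(0.75 × 0.25/90) = 8.9 points for all 90 couples. That is acceptable for a descriptive indicator, provided the interval is shown beside each percentage.
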